- Identify any reasonably foreseeable risks for subjects – the risk (even with an informed consent waiver) are minimal. All of the interventions clinically are not part of this study. This is not research on pregnant women, per se, as the patient is no longer pregnant at the time she is randomized and the incisional bandage is placed. Thus there will be no risk to the developing fetus. There is no effect on lactation and thus there is no risk to the newborn.
- We minimize risks to patients as a matter of surgical principal by using typical sterile technique. We also minimize risks by removing all the bandages by the time the patient leaves the hospital so that way each incision is evaluated prior to the patient leaving. The alternative would be to wait until a clinic visit 1 week later (except for the gauze bandage), however we felt we would standardize and protect our patients best by removing the bandages prior to leaving. In our practice we found that many patients were non-compliant with care of 1-week bandages (bandages that go home with the patient and are removed after 1 week) and thus we do not want to keep the proposed bandages on for 1 week.
- There is a risk that patient data may be lost or viewed by others, however it is quite low as data will be password protected and encrypted as noted above. Furthermore patient identifiers will not be part of the data analysis and will be kept in a separate log. See Data Confidentiality and Privacy section.
- The direct benefit of the research is we can implement the lowest risk infection prevention bundle possible for cesarean sections; if there is no observable clinical difference then we can take into account the cost differences. Recently we tried switching the type of negative pressure wound therapy device we used (from a 3-day version to a 7-day version that is less expensive and smaller); our infection rate changed and we do not know if it is due to confounding or due to the device change – in hind sight we wish that we studied in the same way as proposed here to control for confounding variables.
- The benefit to society is it will identify a way to help bring surgical site infections to zero; while this seem unattainable at times, with each incremental change we get closer to providing that. Additionally this study would help decrease the cost of healthcare by helping obstetricians select the most effective but lowest-cost (short term at time of application) device. If the study demonstrates that a more expensive option is most effective then it can help obstetricians make the case to their hospitals that the extra expense might be revenue neutral or save money in terms of preventing complications.

7. Data Confidentiality and Privacy

- Identifiable PHI will be kept in a data table separate from the remainder of the analyzed data. Additionally it will be maintained in the same PHI-protective required ways that HealthPartners requires. This includes using encrypted hard drives (in case of theft), password protected operating systems (in case of unauthorized access), and on HealthPartners computers whenever possible. We plan to partner with HealthPartners institute for data analysis so when sending email with the non-PHI containing data tables the information will stay within HealthPartners secure email system. Patient information will also be aggregated in the analysis, which will help maintain patient confidentiality when it comes to presenting our data in public for poster presentation and research papers. A study ID will be used on most of the spreadsheets / databases in order to help protect patient MRN from being divulged.
- Since the patient's name and DOB will not be stored it will be difficult to cause harm with to a patient if data is somehow divulged. Since the only patient identifiable information would be stored in a table with only a study ID. If the MRN were released then somehow people would have to have access to HealthPartners systems to compromise that data. This still should not happen.
- Study identifiers would be destroyed upon publication in compliance with a peer-reviewed journal's policy. PHI/study identifiable information would be easy to destroy as it would be kept in a different spreadsheet / database from the main study data. It would also be electronic so it could be destroyed with just a few buttons being pressed and without a trail.

8. Timeline

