
2. Study aims

- Our research question is which of our current practices of covering cesarean section incisions is 1) most clinically effective at eliminating surgical site infection and 2) is most cost effective. Patient safety is paramount and we would want to use the most effective form of surgical site infection prevention bandage/covering – however we do not know which of our practice is more effective. This question is unique to both high risk patients (BMI = or > 40), which uses one type of covering versus our normal risk patients (BMI < 40).
- Our hypothesis is that a sterile silver impregnated silicone foam dressing (Mepilex Border Post-Op Ag) will be effective in maintaining a low surgical site infection rate in both high risk patients (BMI = or > 40) as well as in normal risk patients (BMI < 40). We believe using the Mepilex bandage will be a more cost effective strategy.
- Post-operative surgical site infections are uncommon in our practice (about 1%) they are clinically and financially significant complications of surgery. Strategies to minimize this known complication are essential. Our study is largely exploratory in that there aren't any adequate head-to-head studies that can help us guide our practice in selecting a wound-cover following cesarean.
- The primary clinical aim of this project is to compare and differentiate infection rates between our current two practices. The first practice that many of our OB/GYNs have selected (as part of their clinical practice, not this study) is prophylactic negative pressure wound therapy dressing (wound vac) in high risk patients (BMI = or > 40) and a standard sterile dressing in women who are normal risk (BMI < 40). This change in addition to our surgical site bundle have shown dramatic decreases in surgical site infections and many of our doctors want to continue

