on our success. Several other OB/GYNs have decided to switch to use a different approach (as part of their clinical practice, not this study) and use a silver impregnated silicone dressing (Mepilex Border Post-Op Ag) regardless of BMI. The study will focus on women who have had a cesarean section at Regions Hospital. There have been conflicting data on whether the wound vac strategy is more effective or similarly effective to not using a wound vac; there have been a paucity of research studies that look at this data. There is only a single study that is prospective and it is inadequately powered; the rest are retrospective studies that have conflicting results. There have been no head-to-head comparisons in the class of Mepilex and Mepilex-related products versus prophylactic wound vacs. Our doctors are already using the two sets of products however it is not currently being studied.

- The primary analytic goal of the project will be to look at the cost of the current practice and compare it to the cost of the proposed new practice/comparison practice both with and without incorporating the approximate costs of complications in the bullet point noted above. This is one of the most important points that our study will address, as it will help provide data to inform the fiduciary responsibility of obstetricians in caring for their patients. We will obtain national averages and multiple it by the number of additional patient encounters related to complications; additionally we will obtain billing information of patients with infectious complications to analyze actual differences in cost. We will also collect ICD-10 and CPT codes for hospital, lab and clinic bills during the hospitalization and the subsequent 30-day postoperative period. As part of the data abstraction, these items will be reviewed by two members of the study team to evaluate whether the costs are related to wound care and complications versus routine care. Toes will be broken by a third study team member. We will also analyze the total cost of care in the two groups.
- The secondary clinical goal is to compare the location of the infections (cellulitis, which is easily treated and shallow, versus an abscess; the different locations result in dramatically different treatment intensities such as outpatient antibiotics for simple cellulitis versus invasive inpatient drainage procedures for a complex abscess).

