- An additional secondary clinical goal is to compare the cost of treating the infections by approximating the cost of inpatient stays, outpatient visits, hospital procedures and antibiotics given.
- An additional secondary clinical goal will be to look for complications of the types of post-operative bandages (gauze bandage vs negative pressure wound therapy dressing vs silver impregnated silicone foam bandage).

3. Background, Rationale, Significance

- Post-operative wound infections are a clinically significant and sometimes life-threatening complication of abdominal surgery. Each type of surgery has different risk factors for infection. The vaginal space has its own colonization of bacteria that ascend through the cervix (the "birth canal") into the uterus and exit through the uterine incision into the abdomen. This causes a type of "contamination" that is inherent to cesarean sections not encountered in other types of surgery. Morbidity from cesarean section infections varies from minimal interference to life-threatening and costly. Some infections can be treated with opening up an abscess in the clinic, others with antibiotics and some with hospitalization, which can include IV antibiotics, invasive procedures to drain infectious material or surgery. Each infection costs hundreds to thousands of dollars depending on the type of treatment needed. Minimizing infection is imperative in all patients.
- Obesity is a risk factor for abdominal incision infection, cesarean section is no different. Rates of obesity have been increasing for decades in the United States. As a major trauma hospital, Regions is a referral center for many patients with comorbid conditions too high risk for many community hospitals; obesity is no exception. We need to be vigilant in finding the safest surgical covering in our highest risk patients.

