- Our first of two strategies that our OB/GYNs use relies on negative pressure therapy (wound vacs) in high risk patients. We do not currently use it on obese patients (BMI > or = 30 and < 40), we do use it on patients with morbid obesity (BMI > or = 40). We use standard bandages for patients that are not morbidly obese (BMI <40), which generally is a sterile gauze. Recently our many of the OB/GYNs in our group have decided a more cost effective strategy based on high expenses from the wound vacs based on national trends with OB/GYNs as well as success in Regions Hospital with low post operative wound rates; the use the Mepilex Border Post-Op Ag dressing. The OB/GYNs who have continued with the wound-vac based strategy did not want to switch dressing types and are interested on building on our group's demonstrated improvement. In 2018 about half of our infections were in high-risk patients and half were in low-risk patients. Our infection rate is about 4-10 / 500 =

0.8-2% (annual volume is about 500 cesarean sections); we consider this to be good relative to national averages (5-10%). Our goal is 0%.

- Because post-operative infections are relatively rare the effects of bandages cannot be easily determined without a research protocol to control for confounding variables. In our goal of doing no harm our goal post-operative infection rate is 0%. We would like to systematically approach methods to help us achieve this goal.
- We use surgical site infection prevention bundles to help prevent infections including a preoperative wash, a surgical sterilization/prep, sterile technique, pre-operative antibiotics and sterile abdominal dressing. Our practices change with time and the only way to know the effect of one particular change in this overall uncommon (but clinically salient) complication is to study it; fortunately we are already practicing and collecting data in a way that studying these effects would not affect our patients.
- The negative pressure therapy costs \$300-500 per patient. A standard bandage is <\$4. A silver impregnated silicone post-op dressing costs \$20. This study would help address whether using a silver impregnated silicone foam would be cost effective in all patients or just in the high-risk population. If used universally savings in the high risk group could offset increased costs in the low risk group; costs are generally incurred by the hospital and not billed to the patient.

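### The aim is cost effectiveness, but the planned analysis compares costs only: cost and infection differences are never joined, and the cost difference has no stated interval

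*Combined protocol and SAP*

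**What the plan says.** Section 2 puts two questions about the dressing practices, which is best at "eliminating surgical site infection and 2) is most cost effective". Section 3 repeats the economic question by BMI group: "whether using a silver impregnated silicone foam would be cost effective in all patients or just in the high-risk population".

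The analysis offered for it is the primary analytic goal in section 2, to "look at the cost of the current practice and compare it to the cost of the proposed new practice/comparison practice". This is to be done in two versions, one that counts what complications cost and one that leaves them out. The same paragraph adds: "We will also analyze the total cost of care in the two groups". A secondary goal approximates what treating the infections costs, and section 4.e multiplies billing averages by the extra visits, admissions and procedures.

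Infection rates are compared separately, as the primary clinical aim. No section combines the two results: there is no cost per infection avoided, no net benefit and no interval for the cost difference.

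**The concern.** A difference in cost answers which practice is cheaper. Cost effectiveness also needs the difference in outcome, and a statement of what is paid for it. Adding complication costs does not close that gap, because it values an avoided infection only at its treatment bill. The protocol itself puts patient safety first and sets an infection goal of zero, so by its own values an avoided infection is worth more than the bill.

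The label matters because cost feeds a decision. Section 2 ranks the cost comparison among the most important things the study will address, section 4.f concedes that the infection comparison may be underpowered, and section 8 expects practice to change within weeks of the analysis. A non-significant infection result and a cost-only comparison could together be written up as a finding of cost effectiveness. Splitting by BMI does not remove the problem, since inside each stratum the comparison is still of cost alone.

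**Working it through.** **The plan's own figure.** The documents give no calculation for the cost comparison. Their only one is for infection rates (4.f): 0.5% against 3%, alpha 0.05, power 80%. With pooled variance, two-sided: n = [1.96 × √(2 × 0.0175 × 0.9825) + 0.842 × √(0.005 × 0.995 + 0.03 × 0.97)]² / 0.025² = 430.7, so 431 per cohort and 862 in total. It reproduces, but says nothing about precision for cost.

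**Inputs from the documents.**
- Section 3, dressing prices: negative pressure 300-500 dollars, silver 20, gauze under 4.
- Section 3, infections: 4-10 per 500 women a year, about half of them at BMI 40 or above.
- Section 3, cost of an infection: "Each infection costs hundreds to thousands of dollars depending on the type of treatment needed".
- Section 4.b: 750 women with follow-up in two cohorts of similar size, so about 375 each.

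**Assumptions, not in the documents.** Cost per infection of 1,000 to 10,000 dollars. Share of women at BMI 40 or above of 15%, giving 0.15 × 375 ≈ 56 and 0.85 × 375 ≈ 319 women per cohort. High-BMI risk is then 2/75 to 5/75, or 2.7-6.7%. Low-BMI risk is 2/425 to 5/425, taken as 0.5-1%. Every infection is given the same cost; letting costs vary would add to the role of chance.

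**Break-even.** Risk difference needed = price gap / cost per infection. The gap at BMI 40 or above is 300 − 20 = 280 to 500 − 20 = 480 dollars. Below BMI 40 it is about 20 − 4 = 16 dollars.

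| Cost per infection (dollars) | Infections per 100 women that negative pressure must prevent, BMI ≥40 | Infections per 100 women that silver must prevent, BMI <40 |
|---|---|---|
| 1,000 | 28-48 | 1.6 |
| 3,000 | 9.3-16 | 0.53 |
| 5,000 | 5.6-9.6 | 0.32 |
| 10,000 | 2.8-4.8 | 0.16 |

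**BMI 40 or above.** Suppose negative pressure prevented every infection. Silver is still net cheaper when its infection count is below (gap × 56) / cost per infection. Exact binomial probabilities: 100% at 1,000 dollars, 83-100% at 3,000, 48-99.6% at 5,000 and 10-81% at 10,000. The figure that would go unreported is the dressing cost per infection avoided: 280/0.067 ≈ 4,200 to 480/0.027 ≈ 18,000 dollars.

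As a check on the BMI share, take equal true risks, 375-500 women per cohort and shares of 10-20%. Infection counts reverse the price ordering in 0% of studies at 1,000 dollars, 0-9% at 3,000, 0-20% at 5,000 and 1-31% at 10,000. With a 5% share the figure reaches 27% at 3,000 and 30% at 5,000.

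**BMI below 40.** Silver looks cheaper when gauze has more than (16 × 319) / cost per infection extra infections: 5.1 at 1,000 dollars, 1.7 at 3,000 and 1.0 at 5,000. If silver has no effect, that happens by chance in 0.2-1.5% of studies at 1,000 dollars and 19-27% at 3,000-5,000. Over 300-450 women per cohort and risks of 0.4-1.25%, the ranges are 0-5% at 1,000, 10-29% at 3,000 and 18-43% at 5,000.

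**The case against.** The strongest reply is that the plan does not ignore effect. Infection rate is the primary clinical aim. Section 6 brings in cost when no clinical difference is observed, and considers the case where the dearer dressing works best and "the extra expense might be revenue neutral or save money in terms of preventing complications". A reader might infer that negative pressure therapy could prevent infections and be reported only as the costlier choice. The documents do not support that: its effect would be reported too, though never joined to its cost. Where price dominates, calling the practice costlier is also a correct result.

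A reader might also infer that the plan would miss a true saving below BMI 40 if silver halved infections. It mostly would not, because at these rates there is usually no saving to miss. Against a 16-dollar gap, halving 0.5% saves 0.0025 × 3,000 = 7.50 or 0.0025 × 5,000 = 12.50 dollars, and halving 1% saves 15 or 25 dollars. Silver is truly costlier in three of those four cases.

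The study calls itself exploratory and a pilot and warns of false negatives. Section 4.e lists a t-test that could be applied to costs. These points soften the consequence. But costs are not named there, no interval is promised, and a pilot label does not make a cost comparison answer a cost-effectiveness question.

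Finally, a ratio is fragile with so few events. If risk is truly halved, the observed risk difference is zero or of the wrong sign in 27.6-44.7% of studies at BMI 40 or above and 30.9-43.6% below. That objection stands, and it shapes the fix.

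**Conclusion.** The mismatch between the stated aim and the planned analysis is in the text and depends on no assumption. Its numerical size does depend on two inputs that the documents lack, the cost per infection and the share of women at BMI 40 or above.

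Within the ranges shown, dressing price largely settles the high-BMI comparison up to roughly 3,000-5,000 dollars per infection and loses its hold by 10,000. It would be too strong to say that price alone decides: that is exact only in the version without complication costs. In the low-BMI stratum, one or two infections fix the sign at 3,000-5,000 dollars, while near 1,000 it takes about five and price decides. The point merits a change before analysis, but it does not invalidate the cost data or the infection comparison.

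**What to change.** In sections 2 and 4.e, define the cost-effectiveness result within each BMI stratum as a pair: mean cost difference per woman (dressing price plus complication cost) and infection risk difference. Give joint uncertainty from a bootstrap over women. If a cohort has no infections in a stratum, the bootstrap cannot vary that arm, so add an exact or score interval for the risk difference.

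Report cost per infection avoided only as a secondary figure, when the costlier dressing has the lower observed infection risk. Otherwise show the joint distribution or state dominance. Describe the cost-only result as less costly and reserve cost effective for the joint result.

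Total cost of care can enter only if billing is obtained for all women. Section 2 promises it for both groups, but section 4.c describes the billing pull only for women with an infection or surgical site complication. Dressing price should come from a price list, since section 3 says such costs generally fall on the hospital and are not billed to the patient.

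The cost is some SAP wording and a short bootstrap on planned data, plus a wider billing query if total cost of care is kept. The downside is wide intervals and a less clear-cut cost conclusion.

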- In the patients who have identified clinically identified infections (based on process identified above via chart abstraction) we will also obtain billing data and insurance payment information to identify the financial implications of the complications. This information will be obtained primarily by the HealthPartners Research Foundation Epic team, who will build an EMR database query to obtain this information.
- All data sources needed for the study are named (e.g., chart review, patient survey, data pull from HP electronic medical record) – all data will be abstracted from clinical EMR / Regions charts. We will also use a log from labor & delivery (all births are written down in a paper register and electronic log [MIDAS]) and compare it to our data to make sure patients are included. The Infection Prevention department also keeps a register of all post-operative infections and we will use this information that is already obtained to make sure our records are accurate (this information is readily made available to our department as it is). Additionally, billing data will be obtained for those patients in whom an infection or surgical site complication occurs to analyze complications.
- The person or job title obtaining each data source:
 - Investigators will review each chart for evidence of surgical site infection or bandage-related complications
 - The investigators in the Infection Prevention department will provide records that they already collect to the investigators to make sure data are accurate and complete
 - HealthPartners Research Institute will use Epic data queries to obtain billing and reimbursement data for patients with surgical site infections / complications. The Research Institute calls the individuals who create these queries programmers and they will work with the PI. They will also compare patients that meet inclusion criteria that have requested to not be included in research to allow us to remove those patients.

ii. Process steps for data acquisition

- All patient contact events involving data collection are described in the order they occur.
 - Patients who enter an operating room at Regions Hospital and have a cesarean section will have the cesarean section as per routine. Part of the routine, obviously, includes that the surgery will conclude and a bandage will be placed.
 - The circulator OR nurses will document the type of bandage placed, which is part of the routine already.

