- Patient's will be informed via standard HealthPartners methods, which includes potential inclusion in research unless they request to be excluded.

Who will provide consent? We will ask for a waiver of informed consent.

How will you ensure that the subject understands the consent? We will apply for a consent waiver. In an opt-out manner if a patient requests to not be included we will respect the patient's privacy in making this decision as part of standard HealthPartners policies.

d. Outcome/endpoint and other variable definitions, and instruments used

Definitions: superficial surgical site infection- defined according to Centers for Disease Control and Prevention criteria as infection involving only the skin or subcutaneous tissue occurring within 30 days of surgery with at least one of the following: 1) purulent drainage from the wound or 2) organism identified by culture or wound deliberately opened by the surgeon. Cellulitis will be evaluated as 1) erythema noted in clinical progress notes with antibiotics administered or 2) diagnosis of cellulitis with antibiotics administered. Our secondary outcome was a composite wound complication, including superficial, deep, or organ-space surgical site infection; wound dehiscence; seroma; or hematoma that occurred within 30 days of surgery. Other secondary outcomes included 30-day readmission, 30-day reoperation, and need for antibiotic treatment for any indication. The chart will be evaluated for nursing or provider notes that indicate problems with the bandage. Chart abstraction will be completed to look for other salient complications or factors that were not predicted. Primary and secondary outcomes will be binary with comments possible. Number of clinical visits for complications, enrollment in home healthcare for wound care and length of hospital visits will be noted.

Chart review form will be electronic, it will have the following elements (there will be 3 charts to protect PHI and to blind the analyst from the intervention), all participants will have a study enrollment number to link the data for appropriate analysis:

First form:

MRN	From EMR
Study enrollment #	From 1-1000

Second form:

Study enrollment #	From 1-1000
Intervention	Binary: cohort 1 vs cohort 2
BMI	BMI rounded to the tenths spot

Third form:

Study enrollment #	From 1-1000
Age	#
Enrolled	Yes / no
Follow-up after discharge from home	Yes / no
Complication noted	Yes / no
Date complication noted	Date

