- Possible biases include that while our study may not be powered to detect a difference, that does not inherently mean that a study does not exist if $p>0.05$. While we may draw conclusion based on this it may be a false negative. Selection bias may occur as our patient population has a tendency to be higher risk in terms of maternal morbidity than in many community hospitals. There may be ascertainment bias by the nursing staff reporting on patient complications and the obstetric team taking care of the patient in the hospital, but after the patient leaves that bias should be significantly decreased as it would take effort from the providers in the clinic to check which study group the patient is in (either accessing data or asking the patient).

5. Setting/Environment/Organizational feasibility

- The study will be conducted at Regions Hospital and otherwise by chart abstraction/review
- Cesarean section are done in the hospital-setting, thus the location is appropriate. We selected Regions Hospital as hospital leadership has already committed to using the incisional coverings despite their costs, thus the study can be completed over a long time course and over an anticipated 1000 patients. Other hospitals have not been systematically willing to use these coverings due to concern for cost; Regions pays for it due to the benefits that we believe have been demonstrated by our organization, which impacts reimbursement and thus this will be overall revenue neutral. Leadership is motivated to have the lowest overall surgical site infection. The Infection Prevention department collects much of the information we are studying and thus with minimal effort the organization will be providing much of the data abstraction.
- The study will fit in with HealthPartners Triple Aim in the following ways. It will improve the health by allowing us to study a change in our practice pattern in a systematic manner and apply the changes to our practice. This will also improve the experience of each new family as complications decrease so the time spent recovering from child birth can be focused on the new family. Finally it will help us improve our fiduciary goals by not just looking at whether infection rates are different but also if there is a significantly different cost-burden with the infections that may be conferred by the different types of incisional coverings.

6. Risks and Benefits

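### The infection-location and infection-cost goals name no denominator; compared among infected women only, severity can point the wrong way, so both should be reported per woman in the cohort

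*Combined protocol and SAP*

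**What the plan says.** **The two goals.** Section 2 (Study aims) states: "The secondary clinical goal is to compare the location of the infections". It contrasts shallow cellulitis with abscess because the treatment burden differs. The next goal reads: "An additional secondary clinical goal is to compare the cost of treating the infections by approximating the cost of inpatient stays", followed by other resource items. Neither sentence says whether the denominator is the infections or all women in the cohort.

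**Billing data.** The cost bullet in section 2 plans to use bills from women with infectious complications to look at real cost differences. Section 4.c.i says: "In the patients who have identified clinically identified infections (based on process identified above via chart abstraction) we will also obtain billing data". Further down it widens this slightly: "billing data will be obtained for those patients in whom an infection or surgical site complication occurs to analyze complications".

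**Motivation.** Section 5, on organisational goals, says the study will ask, beyond the rates, "if there is a significantly different cost-burden with the infections that may be conferred by the different types of incisional coverings".

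**Whole-cohort comparisons also planned.** Section 2 states: "The primary clinical aim of this project is to compare and differentiate infection rates between our current two practices". Its cost bullet compares the cost of each practice with and without complication costs and adds: "We will also analyze the total cost of care in the two groups". Section 4.d states: "Our secondary outcome was a composite wound complication, including superficial, deep, or organ-space surgical site infection; wound dehiscence; seroma; or hematoma".

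**Analysis rules.** Section 4.d makes the primary and secondary outcomes yes/no variables. Section 4.e reports infection rate as a number and proportion, and other categorical data as proportions. It does not mention infection depth.

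**The concern.** Infection arises after the dressing is applied and is the study's main clinical outcome. Women who become infected under one dressing are therefore not the counterparts of those who become infected under the other. A dressing that prevents cellulitis and leaves abscesses unchanged will show a higher abscess share and a higher cost per infection, although no woman is worse off.

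Case mix can shift too. Section 3 says about half of the 2018 infections were in high-risk women, and only one cohort gives those women the wound vac. If that device works, the infected women in that cohort will tend to have lower BMI than those in the other.

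At stake is how the severity and infection-cost results are read. The study intends to change practice on its findings, and a severity table that points the other way from the infection rate could be taken as a harm of the better dressing.

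**Working it through.** **Inputs from the documents**
- Local infection rate (section 3): 4/500 = 0.8% and 10/500 = 2%, which reproduces the plan's range.
- Analysable women (section 4.b.ii): 0.75 × 1,000 = 750. The cohorts are expected to be of similar size, so about 375 each.
- Planning rates (sections 4.b.ii and 4.f): 0.5% and 3%.

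**Assumed inputs.** The documents give no split by depth and no cost by depth; section 3 says only that an infection costs from hundreds to thousands of dollars. The splits and dollar values below are mine, with a range for cost.

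**1. Expected infections per cohort**
- Local rate: 375 × 0.008 = 3.0 to 375 × 0.02 = 7.5.
- Planning rates: 375 × 0.005 = 1.9 and 375 × 0.03 = 11.3.

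**2. Location, assumed counts.** Cohort X has 5 cellulitis and 3 abscess; cohort Y has 1 cellulitis and 3 abscess.
- Abscess share of infections: 3/8 = 37.5% versus 3/4 = 75%.
- Abscess risk per woman: 3/375 = 0.8% in both, a risk difference of 0.
- Cellulitis risk per woman: 5/375 = 1.33% versus 1/375 = 0.27%, a difference of 4/375 = 1.07 percentage points in favour of Y.

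Y is better on cellulitis and equal on abscess, yet looks twice as bad on abscess share.

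**3. When this happens.** With cellulitis risk m and abscess risk s, the share is s/(m + s) = 1/(1 + m/s). It rises whenever a dressing cuts m by a larger relative amount than s, even if s falls too. For example, split the planning rates as 2% + 1% versus 0.25% + 0.25%. The share is 1/3 = 33% versus 0.25/0.5 = 50%, while severe infection per woman is 1.0% versus 0.25%.

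**4. Cost, same counts as step 2**

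| Assumed cost, cellulitis / abscess | Cohort total X, Y | Per infection X, Y | Per woman X, Y |
|---|---|---|---|
| $300 / $2,000 | $7,500, $6,300 | $938, $1,575 | $20.00, $16.80 |
| $500 / $8,000 | $26,500, $24,500 | $3,313, $6,125 | $70.67, $65.33 |
| $500 / $10,000 | $32,500, $30,500 | $4,063, $7,625 | $86.67, $81.33 |

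In the last row, for instance, X is 5 × 500 + 3 × 10,000 = 32,500; 32,500/8 = 4,063; 32,500/375 = 86.67. The direction reverses only in the per-infection column. Totals and per-woman means agree with each other.

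**5. What a test could show.** For 3/8 versus 3/4, the two-sided Fisher p is (15 + 120 + 120 + 15)/495 = 0.55. For true severe shares of 33% versus 67%, Fisher's test at 0.05 has about 4% power with 4 infections per cohort and about 17% with 8.

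**The case against.** The strongest reply is that the plan nowhere commits to an infected-only analysis. Outcomes are yes/no variables and the chart form is kept for every study number, which suits abscess yes/no over all women as well as it suits a share of infections. Cost per infection is never named. Sections 2 and 4.e multiply average costs by extra visits, admissions and procedures, which can give cohort totals, and step 4 shows that totals do not reverse. Restricting the billing pull to women with infections or complications proves nothing either, since a per-woman mean with zeros for everyone else uses the same bills. The study also calls itself exploratory and a pilot.

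Much of this stands. A reader might infer that the plan prescribes a comparison of mean cost among infected women, or that section 5 would credit such a difference to the dressing. The documents do not support that: no denominator is fixed, and the section 5 sentence is hedged motivation, not an analysis rule.

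The reply does not settle the location goal. The infected-only reading is the natural one, and nothing in the plan supplies the alternative. The composite in section 4.d pools all depths with dehiscence, seroma and hematoma, so it cannot show whether abscesses in particular became more or less frequent per woman.

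**Conclusion.** The point holds as an unstated denominator whose natural reading conditions on the outcome. It applies mainly to the location goal. In the example the abscess share doubles (38% to 75%) at an identical 0.8% risk per woman. That rests on assumed counts; the reversal requires a dressing to reduce cellulitis proportionally more than abscess, which may or may not occur.

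The cost goal is less exposed, because practice costs and total cost of care are also to be compared across whole cohorts. One caution is that section 4.c.i pulls billing only for women with infections or complications. That does not clearly supply a total-cost comparison, so it should be reconciled with section 2.

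A reader might also infer that the severity results will contradict the infection rates. The documents do not support that either. With about 3 to 7.5 infections per cohort, a test would seldom flag anything; the realistic risk is that bare percentages are over-read. This is an inexpensive improvement to secondary goals and leaves the primary comparison untouched. It also does not remove confounding by surgeon, which affects per-woman comparisons too.

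**What to change.** In sections 2 and 4.e:
- **Location.** Report cellulitis, abscess, deep infection and organ-space infection each as number over all analysed women in the cohort, with risk differences and confidence intervals by a method suited to small counts, overall and by BMI stratum.
- **Cost.** Report infection-treatment cost as a mean per woman, with uninfected women at zero, overall and by BMI stratum, next to the planned total-cost comparison.
- **Infected-only summaries.** Label any share of infections or cost per infection as descriptive, with no between-cohort test.

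The cost is a few sentences. The third chart form already holds complication type and visits by study number, the second holds cohort and BMI, and the planned billing pull covers infected women. One small edit would help: cellulitis is defined in section 4.d but is not among the complication types listed on the form, so it should be added as an entry.
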